**Aim 1: Evaluate RIMO's direct effect on linkage to MAT, length of time on MAT, dropout, and total days of MAT.**

H1: Relative to the control group, RIMO will have a direct effect on: a) initiating MAT sooner, b) staying on medication longer, c) reducing dropout, and d) receiving more total days of MAT.

**Aim 2: Evaluate RIMO's direct and indirect (via MAT) effects on time to relapse, opioid use, and opioid-related overdose.**

H2: RIMO will have direct and indirect (via days of MAT treatment) effects on: a) time to relapse, b) days of opioid use, and c) number of overdoses.

**Aim 3: RIMO's direct and indirect (via MAT and opioid use) effects on opioid-related fatalities, OUD symptoms, physical health, mental health and the cost of health care utilization.**

H3: RIMO will have direct and indirect (via days of MAT treatment and days of opioid use) effects on: a) opioid-related fatalities, b) opioid use disorders symptoms, c) physical health, d) mental health, and e) cost of health care utilization.

Referral Only Control. During the phase 1 pilot, we collaborated with our study partners as well as the Illinois Opioid STR partners to develop a brochure that includes a list of MAT providers in Chicago, and their location, telephone number, hours of operation, adjacent bus lines, and type of funding accepted (e.g., Medicaid). In addition, the brochure includes a range of other SUD treatment options (e.g., residential or outpatient drug-free treatment), including office-based physicians who prescribe buprenorphine or other forms of MAT. This brochure is will be given to participants in both groups at the baseline assessment. Research staff will follow a script that does not include any statements regarding motivation for treatment. At present, based on our interviews with key informants and focus group with pilot study participants, there is currently no systematic method in place for referring individuals to MAT (or other SUD treatment) either from the first responders following administration of naloxone or at the EDs following their admission for opioid-related overdose. Hence, this condition represents more than the “usual care” in the community.

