Opioid Related Fatality: Any ICD-10 cause of death related to opioid overdose (T40.1, T40.2, T40.3, T40.4, T40.6, X42, X44, X62, X64, Y12, Y14) in CDC death records.		O	
Opioid Use Disorder: The average of 11 past 90-day items on the Opioid Use Disorder Scale (11 DSM-5 symptoms) self-reported from the GAIN-Q3 follow-up interviews			O
Physical Health: The average of 5 past 90-day items on the Health Problem Screener (worried about health, pain, health kept participant from meeting responsibilities) from GAIN-Q3 follow-up interviews.			O
Mental Health: The average of the past 90-day items across the Internalizing (symptoms of depression, anxiety, trauma, suicide) or Externalizing (symptoms of attention deficit, hyperactivity, conduct, gambling) Disorder			O
Cost of Health Care Utilization: Sum of the quarterly costs of health care from the GAIN-Q3 follow-up interviews; based on the frequency of health, mental health or substance-related ED visits, hospitalizations, residential treatment, outpatient surgery, MAT, intensive outpatient, outpatient treatment days/times multiplied by their respective costs using published estimates by health economists, adjusted for inflation using the CPI.			O
Key: R=Randomization, O=Outcome, M=Mediator			

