### 4. Sample size and power calculation

We plan to recruit and randomize 350 participants over 24 months. There should be 99% or more power to determine the direct effect of RIMO on the primary outcome of time to MAT initiation (H1a) assuming a sample size of 350 patients, randomized into two groups of 175 each, interviews at 4 time points for the main analysis (baseline, and 3, 6, and 9 months post-randomization), our average completion rate of 94+% per follow-up wave, and a moderate to large effect size of  $d=3.0$ . This expected effect size was based on the natural log of the odds ratio ( $\text{Log}^e(\text{OR})=d$ ) of initiating MAT ( $\text{OR}=20.2$ ) from RIMO Pilot study ([name] et al., under review). For the other tests of direct effects, the effective n for power calculations in repeated measures analysis varies between a lower bound of the number of unique people per group ( $N=175$  people), and an upper bound of the number of people randomized plus the completed follow-up interviews or 668 observations per group ( $O=(175 \text{ people at intake} + \text{average of } 94\% \times 175 \text{ people} \times 3 \text{ follow-ups})$ ) as a function of the intra-class correlation coefficient (ICC) associated with the individual and the number of repeated measures (RM) per person ( $\text{effective } n'=O/(1+\text{ICC}(\text{RM}-1))$ ). In our prior studies, ICC of the other dependent

variables ranged from .13 to .34. Thus the effective n= range from 429 to 398 per group and be capable of detecting an effect size of  $d=0.2$  or more with 80% power for a two-tailed test of  $p<.05$  of effect sizes  $d=.2$  or more. For mediation analysis, the tests should also have 80%+ power for a 2-tailed test of  $p<.05$  and an indirect effect size of  $d=.2$  or more.

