Direct Effects of RIMO on MAT (Aim 1). Relative to the referral only control group, the direct effects of RIMO on reducing dropout and receiving more total days of MAT will be evaluated using a multilevel structural equation modeling (MSEM) with mixed effects in MPlus (version 7.4). The analysis will model observations (Level 1) nested within participants (Level 2), with participants modeled as a random factor anchored on the baseline version of the dependent variable. Randomization to RIMO will be modeled as a Level 1 predictor. We will check for the need to use models that adjust for counts or zero saturation.

Direct Effects of RIMO on Secondary Outcomes of Time to Relapse, Opioid Use and Overdose (Aim 2) and Death, OUD, Health, Mental Health, and Health Care Utilization (Aim 3). Relative to the referral only control group, the direct effects of RIMO on time to first relapse (H2) will be evaluated with a survival analysis similar to Aim 1 H1. It will be examined after the point of randomization and after each follow-up interview. The direct effects of RIMO on days of opioid use (H2), opioid overdoses (H2), opioid-related fatality (H3), symptoms of OUD (H3), physical health problems (H3), mental health symptoms (H3), and the cost of health care utilization (H3) will also be evaluated using a series of MSEM with mixed effects in MPlus modeled in the same way as above. Most of the above variables are relatively continuous, but we will check for the need to use models that adjust for counts or zero saturation. For opioid-related fatality (H3), we will define the dependent variable as dichotomous in MPlus (equivalent to using logistic regression).

Indirect Effects of RIMO (Aims 2 and 3). To evaluate indirect effects, we will determine the extent to which the direct effects of RIMO on the above dependent variables are changed by of days of MAT received (H2 & H3) and/or days of opioid use (H3) using the Preacher and colleagues framework for testing mediation in MSEM with REML in MPlus. Loss of statistical significance in the path coefficient from the intervention conditions to the other outcome variables would indicate full mediation; a reduction in the path coefficient would indicate partial mediation. Change will be evaluated using MacKinnon's joint-significance testing of the path *z*-scores with a Sobel test using a standard error based on bootstrapping and criteria of  $p < .05$  on the degree of change.

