#### **21. Process of AE/SAE collection, assessing by PI and/or medical monitor and reporting**

Our study definitions of critical events to be monitored are:

- The expected Adverse Events (AE) measured directly as part of baseline and quarterly observations are the days of problems from AOD use, health problems interfering with responsibilities, mental health problems interfering with responsibilities, being disturbed by memories, behavioral problems, being homeless, family problems, illegal activity, arrests, in trouble with parole/probation.
- The expected Serious Adverse Events (SAE) measured directly as part of the quarterly observation are any medical ER/hospitalization, any mental health ER/hospitalization, and any incarceration. Deaths are documented both in follow-up logs and (if we have firsthand or reliable information) as in the negative event report discussed below.
- Unexpected AE/SAE (including deaths where we have details) will be documented the same day we find out about it with the negative event report. This includes documentation to code who was there, when/how it happened, where it happened, what actions were taken (e.g., referral to clinical supervisor, police report, hotline call).

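### The opioid-fatality definition lists poisoning codes that do not by themselves identify an opioid, and no rule requires an opioid T40 code alongside them

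*Combined protocol and SAP*

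**What the plan says.** Under Aim 3 in Section 1, H3 posits direct and indirect "effects on: a) opioid-related fatalities, b) opioid use disorders symptoms", among other outcomes. The indirect paths run through days of MAT and days of opioid use.

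Table 2.1 (Section 2) gives the operational definition of the first of these: "Any ICD-10 cause of death related to opioid overdose (T40.1, T40.2, T40.3, T40.4, T40.6, X42, X44, X62, X64, Y12, Y14) in CDC death records". It does not say which codes must be the underlying cause and which may be contributing causes. It does not say whether an X/Y code must occur with a T40 code.

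Section 10 adds only the form of the variable: "For opioid-related fatality (H3), we will define the dependent variable as dichotomous in MPlus (equivalent to using logistic regression").

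Section 21 covers deaths as safety events: "Deaths are documented both in follow-up logs and (if we have firsthand or reliable information) as in the negative event report discussed below". It gives no rule for attributing a death to an opioid.

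**The concern.** The two halves of the list do different work. The T40 codes identify the substance. The sponsor lists T40.1 to T40.4 and T40.6 but leaves out T40.5, the cocaine code, which suggests that non-opioid drugs are meant to stay out.

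The X and Y codes record intent and a broad drug group. In ICD-10, the classification that the definition invokes, X42, X62 and Y12 cover narcotics together with psychodysleptics, a group that includes cocaine. X44, X64 and Y14 cover other and unspecified drugs. If one of these codes is enough on its own, it brings back the deaths that the omission of T40.5 appears to exclude.

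H3a will probably rest on few deaths, so one or two reclassified deaths can move the estimate. Poisoning deaths without an opioid, if RIMO does not affect them, pull the ratio towards 1. The plan also leaves the choice open: one analyst could score X44 alone and another could insist on a T40 code, each believing the definition was followed. That should be settled before death records are linked.

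**Working it through.** **Inputs from the documents.** The code list is in Table 2.1 and the dichotomous analysis is in Section 10. Section 4 gives 350 participants "randomized into two groups of 175 each". The plan states no fatality rate, expected number of deaths or fatality-specific power, so there is no figure of its own to reproduce. The power statements in Section 4 concern time to MAT initiation, repeated-measures outcomes and mediation.

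**Input from the classification.** The documents do not print the code titles. Their meaning is taken from ICD-10.

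**Assumptions.** None of these is in the documents:
- A share q of 5%, 10% or 20% of control-arm scored deaths involves no opioid.
- The true opioid-fatality ratio is 0.60.
- RIMO does not change the non-opioid deaths.
- The arms are equal in size.
- Ten deaths are scored in total.

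**Step 1: apply the list literally.** The records are constructed to test the rule and are not observed data.

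| Codes on record | Any listed code? | Listed T40 code? |
|---|---|---|
| X42 + T40.1 | yes | yes |
| X42 + T40.4 + T40.5 | yes | yes |
| X42 + T40.5 | yes | no |
| X44 + T50.9 | yes | no |

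The last two records score as opioid fatalities with no opioid recorded.

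**Step 2: dilution of the ratio.** Observed ratio R = 0.60 × (1 − q) + q.
- q = 5%: 0.57 + 0.05 = 0.62
- q = 10%: 0.54 + 0.10 = 0.64
- q = 20%: 0.48 + 0.20 = 0.68

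**Step 3: miscounted deaths.** With 10 scored deaths, the control arm has C = 10/(1 + R). The non-opioid deaths are equal in the two arms, so their total is 2 × q × C.
- q = 5%: C = 10/1.62 = 6.17; 2 × 0.05 × 6.17 = 0.6
- q = 10%: C = 10/1.64 = 6.10; 2 × 0.10 × 6.10 = 1.2
- q = 20%: C = 10/1.68 = 5.95; 2 × 0.20 × 5.95 = 2.4

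**Step 4: compare with sampling error.** Ten deaths at a ratio of 0.60 split as 6.25 and 3.75. The standard error of the log ratio is √(1/6.25 + 1/3.75 − 2/175) = 0.644. The 95% interval is 0.60 × exp(±1.96 × 0.644), or about 0.17 to 2.1.

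**Step 5: power, on a second set of assumptions.** Take a control opioid-death risk of 4%, a true ratio of 0.50, 175 per arm and a two-sided 0.05 test of two proportions (normal approximation, rough with so few events). Without non-opioid deaths, 175 × (0.04 + 0.02) = 10.5 events are expected and power is about 19%. With a 20% share, each arm gains a risk of 0.04 × 0.20/0.80 = 0.01. The risks become 0.05 and 0.03, the ratio 0.60, the events 14.0 and the power about 16%.

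**The case against.** The opening words of the definition already limit it to causes related to opioid overdose. On that reading the X/Y codes only describe the manner of an opioid death, and the omission of T40.5 supports it. This part of the objection stands: a reader might infer that the plan definitely counts cocaine-only deaths as opioid fatalities, and the text does not establish that. It shows that the literal list would do so and that no stated rule prevents it.

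The population also matters. Section 3 requires a naloxone-reversed opioid overdose within the past week and a positive OUD screen. Many X42 or X44 deaths in this cohort would probably involve an opioid even if the certificate names none. The true share could therefore lie at or below the low end of the assumed range, and a strict T40 requirement would drop some real opioid deaths from the main count. This also stands, and it is the reason for the sensitivity analysis.

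The assumption that RIMO leaves non-opioid deaths unchanged may overstate the dilution, because Section 1 describes linkage work on alcohol and other substance use as well.

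Finally, a shift from 0.60 to between 0.62 and 0.68 lies far inside an interval of 0.17 to 2.1, and power is low under either definition. A reader might infer that the code list threatens the trial's conclusions. It does not: Section 10 makes time to MAT initiation the primary outcome, and the stopping rule in Section 20 does not name fatality. None of this supplies the missing rule.

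**Conclusion.** The point holds as a defect in the definition of one secondary outcome. The list mixes codes that identify an opioid with codes that do not, and no co-requirement joins them. Applied as written, it can score deaths with no opioid recorded.

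How often this would happen cannot be known from the documents, and it may be rare. The attenuation from 0.60 to 0.62–0.68, and the 0.6 to 2.4 miscounted deaths, rest entirely on the assumptions listed with the calculation. They show direction and scale and do not predict a result. The effect on the indirect paths has not been quantified. The reason to act is that the correction is cheap and removes an analyst's choice before the death data are seen. Priority is low.

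**What to change.** In Table 2.1, replace the any-code wording with a two-part rule: a listed drug-poisoning X/Y code as the underlying cause, and at least one of the listed opioid codes (T40.1 to T40.4, T40.6) among the multiple causes of death. State that an X/Y code alone does not qualify. Name the multiple-cause fields of the CDC death records as the source. Report X/Y deaths without a listed T40 code separately, and add them to the outcome in a sensitivity analysis.

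Keep to the sponsor's T40 codes. Adding T40.0 would be a separate change that needs its own justification. T40.6 also covers unspecified narcotics and so is less specific than the others, but it is already on the list.

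The cost is a small edit to the table and one extra analysis, using fields of the same death records. The downside is that opioid deaths certified without a named drug move from the main definition to the sensitivity analysis. If such deaths are lost at the same rate in both arms, the main analysis loses events but the expected ratio does not shift. Deaths that RIMO does not affect, when counted, pull the ratio towards 1.

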### 3. Inclusion and exclusion criteria

The study will target individuals who have received naloxone administered by first responders within the past week to reverse an overdose, but who have not entered into MAT. Inclusion criteria are: a) experienced an opioid overdose reversed with naloxone administered by first responders on a participating team within the past week, b) not in treatment during the past 30 days, and c) screen positive for an OUD. For logistical reasons, we will exclude anyone who is: d) under age 18, e) unable to speak and understand English, f) not residing in Chicago, or g) cognitively unable to provide informed consent.

### 4. Sample size and power calculation

We plan to recruit and randomize 350 participants over 24 months. There should be 99% or more power to determine the direct effect of RIMO on the primary outcome of time to MAT initiation (H1a) assuming a sample size of 350 patients, randomized into two groups of 175 each, interviews at 4 time points for the main analysis (baseline, and 3, 6, and 9 months post-randomization), our average completion rate of 94+% per follow-up wave, and a moderate to large effect size of  $d=3.0$ . This expected effect size was based on the natural log of the odds ratio ( $\text{Log}^e(\text{OR})=d$ ) of initiating MAT ( $\text{OR}=20.2$ ) from RIMO Pilot study ([name] et al., under review). For the other tests of direct effects, the effective n for power calculations in repeated measures analysis varies between a lower bound of the number of unique people per group ( $N=175$  people), and an upper bound of the number of people randomized plus the completed follow-up interviews or 668 observations per group ( $O=(175 \text{ people at intake} + \text{average of } 94\% \times 175 \text{ people} \times 3 \text{ follow-ups})$ ) as a function of the intra-class correlation coefficient (ICC) associated with the individual and the number of repeated measures (RM) per person ( $\text{effective } n'=O/(1+\text{ICC}(\text{RM}-1))$ ). In our prior studies, ICC of the other dependent

variables ranged from .13 to .34. Thus the effective n= range from 429 to 398 per group and be capable of detecting an effect size of  $d=0.2$  or more with 80% power for a two-tailed test of  $p<.05$  of effect sizes  $d=.2$  or more. For mediation analysis, the tests should also have 80%+ power for a 2-tailed test of  $p<.05$  and an indirect effect size of  $d=.2$  or more.

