## **2. Primary and secondary objectives and outcome measures**

The primary outcome measure for the study is the GAIN-Quick Version 3 (GAIN-Q3). The GAIN-Q3 includes 4-6 symptom count screeners that are correlated .9 or more with the 11 to 43-symptom version in the full GAIN. It also has cut points with excellent (~90%) sensitivity, specificity, and area under the curve (AUC) relative to the full GAIN in 9 problem areas related to substance use disorders, physical health, internalizing and externalizing mental health disorders, as well as school, work, stress, HIV risk behaviors/victimization, and crime/violence. The days of use measures have been validated against the Timeline Follow-back, collateral reports, and urine and saliva tests. The GAIN-Q3 also includes summary measures for health care utilization, functional impairment, quality of life, and life satisfaction. The GAIN-Q3 includes the behavioral health screener and health care utilization measures that have been recommended by NIH's Phenx common data elements as two of the most reliable, valid, efficient, and inexpensive tools in the field. At each follow-up, the Q3 follow-up will be supplemented with a) a section on overdose and naloxone experiences, and b)

symptom counts from the OUD scale. Table 2.1 crosswalks the key independent measures and secondary outcomes from the hypotheses to their definitions, reliability, data sources, and the specific aims they address.

Table 2.1. Crosswalk of Variables, Definition, and Aims	H1	H2	H3
Experimental Assignment: Based on computer-generated urn randomization, participants will be assigned to the referral only control group or the experimental RIMO condition.	R	R	R
MAT Time to Initiation: Days from index naloxone administration to the initiation of any kind of MAT, from treatment records.	O		
Length of Staying on Medication: Days between MAT initiation and discharge, from treatment records.	O		
MAT Days: Total days of MAT over 9 months from GAIN-Q3 and treatment records.	O	M	M
Time to Relapse: Days from randomization to next subsequent use of opioids or heroin based on GAIN Q3 follow-up interviews and urine tests.		O	
Opioid Days of Use: Days of opioids and/or heroin use summed over the GAIN-Q3 follow-up interviews.		O	M
Opioid Overdose: Number of opioid-related overdose[s] summed over the GAIN-Q3 follow-up interviews.		O	

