## **10. Statistical analysis plan**

Missing data. Participants will complete their baseline interview prior to randomization. Based on prior studies conducted by the applicants, it is expected that approximately 90% or more of the 3, 6, and 9-month post-randomization interviews will be completed. Among these completed interviews, prior studies conducted by the team indicate that less than 1% will have additional missing data on any of the core items required to test the study hypotheses. Multiple imputations will be used to replace the small amounts of missing data to allow the least biased estimate for each analysis. To further reduce potential bias, analyses will be rechecked by running them without missing data. If there are any clinically significant differences ( $d > |.2|$ ), a general latent variable framework will be used to analyze non-ignorable or systematic missing data that tests whether missing data is qualitatively different by condition.

Survival Analysis for Time to MAT Initiation and Time on Medication (Aim 1). The primary outcome is the days from randomization until the initiation of any kind of MAT. Relative to the referral only control group, the direct effects of RIMO on reducing the days from randomization to initiation of any MAT (H1a) and increasing the days on medication after initiation (H1b) will be evaluated with a Cox Regression model using IBM SPSS version 24 with random assignment to RIMO as the main predictor, as the investigators have done in earlier experiments. It will be examined after the point of randomization and after each follow-up interview. Survival analysis incorporates information about censorship (e.g., death, people who were not admitted to MAT within 9 months) and can incorporate covariates if needed. The output includes a case summary (e.g., missing data, other problems, descriptive statistics) and an evaluation of each term (e.g., beta, its standard error, Wald, its probability, the odds ratio, the 95% confidence interval for the odds ratio). The beta can also be converted to a Cohen's effect size *d*. All analyses will use an intent-to-treat approach (i.e., participants are analyzed as assigned regardless of their actual level of participation in RIMO). We will also conduct a secondary analysis of the time to MAT initiation after each RIMO checkup to understand the pattern over time as we have done with earlier experiments.

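### The repeated-measures power claim in Section 4 (80% at d=0.2 from 398-429 per group) cannot apply to H1b, time on medication after starting MAT, which needs its own event-based figure

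*Combined protocol and SAP*

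**What the plan says.** Section 1 (Aim 1) lists staying on medication longer (H1b) among the direct effects of RIMO. Section 4 first gives a separate power figure for H1a, time to MAT initiation. It then turns to everything else: "For the other tests of direct effects, the effective n for power calculations in repeated measures analysis varies between a lower bound of the number" (people, 175) and an upper bound built from the interviews, "or 668 observations per group". It applies an ICC-based reduction and concludes: "Thus the effective n= range from 429 to 398 per group and be capable of detecting an effect size of" d=0.2 with 80% power, two-sided .05. Apart from a sentence on mediation, Section 4 has no other power figure.

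Table 2.1 in Section 2 defines the H1b outcome as "Days between MAT initiation and discharge, from treatment records". Section 10 places it in the survival analysis: "increasing the days on medication after initiation (H1b) will be evaluated with a Cox Regression model". The multilevel repeated-measures model, described in the following paragraphs of Section 10, is used for dropout, total days of MAT and most later outcomes, not for H1b. Section 10 also says that all analyses are by intent to treat, and gives no rule for people who never start MAT.

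**The concern.** The effective n in Section 4 exceeds the number of people randomised because each person contributes up to four interviews. H1b has no repeated interviews. It is one duration per person, and the clock starts only when MAT starts. In a Cox model the information comes from discharges, and a person who never starts has no time at risk. Neither the observation count nor the ICC formula describes that analysis.

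The planning effect for H1a makes this worse. An OR of 20.2 for starting MAT means that starters would be unevenly split between arms, and the smaller side limits H1b.

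H1b is one of four Aim 1 hypotheses. A reader who relies on the 80% could take a non-significant H1b as evidence that RIMO does not lengthen time on medication, when the design may have had little chance of showing the stated effect.

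**Working it through.** **Inputs from the documents.** Section 4: "randomized into two groups of 175 each"; "our average completion rate of 94+% per follow-up wave"; "interviews at 4 time points for the main analysis (baseline, and 3, 6, and 9 months post-randomization"); ICC .13 to .34; OR 20.2; d=0.2; two-sided .05. Section 1: pilot arms of 16 (RIMO) and 17 (control), with the OR for any MAT taken at 30 days.

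**Assumptions, not in the documents.** The control start rate over 9 months, the fraction of starters discharged, and the conversion from d to a hazard ratio. Section 10 says a Cox beta can be converted to d but gives no formula. Three conversions are used:
- |ln HR| = d = 0.20, in the style of Section 4's log-ratio rule
- 0.2 × π/√6 = 0.257, for exponential times
- 0.2 × π/√3 = 0.363, the logistic conversion

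**1. The plan's figure.** A two-sample comparison at d=0.2 has 80.5% power with 398 per group and about 83% with 429. The printed 80% therefore rests on the repeated-measures n. (Separately, the plan's formula with O = 175 + 0.94 × 175 × 3 = 668.5 gives 668.5/(1 + .13 × 3) = 481 and 668.5/(1 + .34 × 3) = 331, not 429 and 398. That does not affect the present point.)

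**2. Upper bound for H1b: everyone starts and everyone is discharged.** By Schoenfeld's formula, power = Φ(√(D·p·(1−p)) × |ln HR| − 1.96) plus a negligible other tail. D is the number of discharges and p the share in one arm. With 175 per arm, D·p·(1−p) = 350 × 0.25 = 87.5, and its square root is 9.354.
- ln HR 0.20: 1.871 − 1.96 = −0.089, power 46%
- ln HR 0.257: power 67%
- ln HR 0.363: power 92%

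A two-sample comparison of 175 v 175 at d=0.2 also gives 46%. With ln HR 0.20 and equal arms, 80% power needs about 785 events, against 350 people randomised.

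**3. With OR 20.2 over follow-up.** RIMO start rate = 20.2 × odds / (1 + 20.2 × odds), where odds are those of starting in controls. For 20% of controls: odds 0.25, so 5.05/6.05 = 0.835. That gives 35 v 146.1 starters. If all are discharged, D·p·(1−p) = 35 × 146.1/181.1 = 28.2, root 5.31. At ln HR 0.20, 1.06 − 1.96 = −0.90, which is 18.6% with the other tail.

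| Control start (assumed) | Starters, control v RIMO | Discharged | Power, ln HR 0.20 | 0.257 | 0.363 |
|---|---|---|---|---|---|
| 10% | 17.5 v 121.1 | 100% | 12.2% | 17.1% | 29.4% |
| 10% | 17.5 v 121.1 | 70% | 10.0% | 13.4% | 22.1% |
| 20% | 35 v 146.1 | 100% | 18.6% | 27.6% | 48.7% |
| 20% | 35 v 146.1 | 70% | 14.4% | 20.7% | 36.4% |
| 30% | 52.5 v 156.9 | 100% | 24.1% | 36.3% | 62.4% |
| 30% | 52.5 v 156.9 | 70% | 18.3% | 27.0% | 47.8% |

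With every starter discharged, the |ln HR| detectable at 80% power is (1.96 + 0.84) divided by the root above: 0.72, 0.53 and 0.45 for 10%, 20% and 30% control start. These are hazard ratios for discharge of about 0.49, 0.59 and 0.64.

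**4. A check on the assumed start rate.** With pilot arms of 16 and 17, the only whole-number table whose raw OR rounds to 20.2 is 13/16 v 3/17: (13 × 14)/(3 × 3) = 20.22. Scaled to 175 per arm this is about 142 v 31 starters, with power 17%, 25% and 45% under the three conversions if all are discharged. This supposes an unadjusted OR and complete 30-day follow-up.

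**5. Where 80% is reached.** At 50% control start (87.5 v 166.7), all discharged and ln HR 0.363, power is 78%. It crosses 80% at about 53% control start (93 v 168): 92.8 × 167.6/260.4 = 59.7, root 7.73, × 0.363 − 1.96 = 0.84. At 60% (105 v 169) it is 83%. Fewer discharges move the crossing higher. Under the other two conversions it is never reached (step 2).

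**The case against.** The strongest reply is that Section 4 never names H1b. Its sentence speaks of repeated-measures analysis and of the ICCs of other dependent variables, so it may have been meant only for the multilevel outcomes. That is a fair reading of intent. On that reading H1b has no power calculation at all, and the same added line is needed.

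A reader might also infer that OR 20.2 by itself leaves only a few dozen controls in H1b. It does not. An OR fixes no count without a start rate, the plan gives none, and the pilot OR is a 30-day figure from 33 people. More controls may start over 9 months. The counts in the table are conditional on the assumed rates.

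A reader might go further and say that 80% is out of reach unless practically everyone starts MAT. That is wrong: about 53% control start suffices if every starter is discharged and the logistic conversion applies, and this is compatible with OR 20.2.

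Nor does the plan say that H1b is restricted to starters. That follows from the outcome definition, while the intent-to-treat statement leaves non-starters unaddressed. This stands as a gap to settle before any power figure is printed. It does not rescue the printed basis: however non-starters are handled, there is one value per person and at most 175 per arm.

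Finally, no section says that a null H1b will be read as no effect. That is a risk of the printed 80%, not a stated intention.

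**Conclusion.** The concern holds in this form: the 398-429 per group and 80% at d=0.2 cannot be the power basis for H1b, although the wording of Section 4 extends them to it. This part needs no assumed start rate. One duration per person in at most 175 per arm gives 46% or 67% under two of the three conversions even in the most favourable case, and exceeds 80% only under the third.

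The size of the shortfall is conditional. With OR 20.2 over follow-up, 10-30% control start and 70-100% of starters discharged, power is about 10-62%. Higher control start rates narrow the gap.

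The point does not reach the primary outcome, H1a, and does not show that the trial is too small. It concerns one secondary Aim 1 hypothesis whose stated power is unsupported.

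**What to change.** 1. Section 10, first: state which participants H1b includes and how people who never start MAT are handled, consistent with the intent-to-treat statement. The power line depends on this choice.
2. Section 4: exclude H1b from the statement on other direct effects, and give it its own event-based line. That line should state the assumed starters and discharges per arm, the target hazard ratio (with the d-to-HR conversion if d is kept), and the resulting power or detectable hazard ratio. If the sponsor has no basis for a single control start rate, show a range.
3. Section 10, reporting: give the hazard ratio with its confidence interval and the starters and discharges per arm. Say that a non-significant H1b is not evidence of equal time on medication.

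The cost is wording in two sections and one less favourable power figure. Sample size, data collection and procedures do not change.
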